3.5 STOPPING GUIDELINES

The Protocol Chair, the NIAID Medical Monitor and the Data and Safety Monitoring Board (DSMB) will periodically review safety data. If any one of the criteria listed below is met, study enrollment will be suspended and active participants will be maintained on their current immunosuppressive treatment regimens (i.e., withdrawal or discontinuation of immunosuppressive agents will be suspended) pending expedited review of all pertinent data by the NIAID Transplant DSMB, NIAID DAIT and the ITN. Participants who have completed immunosuppression withdrawal may be required to restart immunosuppression depending on the findings of the expedited review.

The criteria described below provide guidance for suspending trial enrollment based on the occurrence of selected AEs. Selected AEs of particular concern and their thresholds in this study are described below. A stopping guideline will be met if either of the following occurs:

1. Rejection resulting in death, re-transplantation, or listing for re-transplantation in any study participant.

2. If the lower bound of the one-sided 90% exact binomial confidence limit for the composite incidence of severe acute rejection and chronic rejection per the Banff global assessment criteria¹⁻³ and steroid-unresponsive (i.e.- ‘refractory’) rejection is greater than 5%.
3. Any grade 4 or higher adverse event attributed to the treatment of rejection or suspected rejection, as assessed by the NIAID Medical Monitor.

For the evaluation of stopping guidelines the rate of the composite outcome will be monitored continuously by the SDCC by estimating the incidence rate and its exact one-tailed lower 90% CI. If the lower CI limit exceeds the threshold, enrollment and further weaning will be suspended pending DSMB review. **Table 2** below gives the minimum numbers of participants with events of each type at which the stopping rules would be met for various numbers which are undergoing immunosuppression withdrawal or have withdrawn.

Table 2. Minimum Numbers of Participants with Events that Trigger DSMB Review and Study Interruption

Number of Participants Undergoing ISW or Have Withdrawn	Minimum Number of Participants with Severe AR, Refractory AR, or CR	Estimated Percentage of Participants Meeting the Stopping Rule	Associated Lower Bound of the Exact One-sided 90% Confidence Interval
10	2	20.0	5.45
20	3	15.0	5.64
30	4	13.3	5.94
40	5	12.5	6.21
50	6	12.0	6.43
60	6	10.0	5.34

AR= acute rejection; CR=chronic rejection

3.5.1 Ongoing Review

The protocol chair, the ITN clinical trial physician, the NIAID medical monitor and the NIAID Transplant Data and Safety Monitoring Board (DSMB) will periodically review safety data. Enrollment of participants in the trial and further immunosuppression withdrawal for current trial participants will be suspended at any time if any of these reviews concludes that there are significant safety concerns.

4. ELIGIBILITY

4.1 INCLUSION CRITERIA

4.1.1 Recipient

Recipient participants *must meet all* of the following criteria to be eligible for this study:

1. At the time of screening:
 - 18 to 50 years old and more than 6 years post-transplant OR
 - Greater than 50 years old and more than 3 years post-transplant
2. Recipient of either deceased or living donor liver transplant.
3. Recipient of single organ transplant only
4. Must have a screening liver biopsy that fulfills the criteria in **Table 3** based on the central pathology reading.
5. Liver function tests (Direct bilirubin, ALT) less than twice the upper limit of normal (ULN). ULN values for liver function tests will be defined by ranges from Harrison's Principles of Internal Medicine, 18th edition.
6. Receiving calcineurin inhibitor (CNI) based maintenance immunosuppression. Participants may also concurrently receive:
 - low dose mycophenolate mofetil (MMF \leq 1500 mg daily) or mycophenolic acid (\leq 1080 mg daily) OR
 - prednisone \leq 7.5 mg daily or equivalent corticosteroid.
7. Ability to sign informed consent

4.1.2 Living Donor

Living donor participants *must meet all* of the following criteria to be eligible for this study:

1. At the time of screening: \geq 18 years old
2. Living donor of the liver allograft of an enrolled recipient participant
3. Ability to sign informed consent
4. Willingness to donate appropriate biologic samples

4.2 EXCLUSION CRITERIA

4.2.1 Recipient

Recipient participants who meet any of the following criteria will not be eligible for this study:

1. History of HCV infection (defined as a positive HCV antibody test)

2. Positive antigen-antibody immunoassay for HIV-1/2
3. Serum positivity for HBV surface antigen or HBV-DNA
4. History of immune-mediated liver disease in which immunosuppression discontinuation is inadvisable (autoimmune hepatitis, primary sclerosing cholangitis, primary biliary cirrhosis)
5. Any medical condition associated with a likely need for systemic corticosteroid administration, e.g., reactive airways disease
6. Prospective baseline liver biopsy showing any of the following: a) acute rejection according to the Banff global assessment criteria¹⁻³; b) early or late chronic rejection according to the Banff global assessment criteria¹⁻³; c) inflammatory activity and/or fibrosis in excess of permissive criteria according to Banff 2012 criteria⁴ (see **Table 3**); d) any other histological findings that might make participation in the trial unsafe. Eligibility will be determined by the findings on the central biopsy reading.
7. Rejection within the 52 weeks prior to screening
8. Estimated GFR <40 ml/min as calculated by CKD-EPI method (to mitigate the risk of worsening renal failure should rejection occur and high level of CNI be required)
9. The need for chronic anti-coagulation that cannot be safely discontinued for a minimum of 1 week to safely perform a liver biopsy
10. Pregnant females and females of childbearing potential who are not using an effective method of birth control
11. Current drug or alcohol dependency
12. Inability to comply with the study visit schedule and required assessments, including frequent liver function monitoring and protocol biopsies
13. Inability to comply with study directed treatment
14. Any medical condition that in the opinion of the principal investigator would interfere with safe completion of the trial
15. Participation in another interventional clinical trial within the 4 weeks prior to screening

Table 3. Screening Biopsy Inclusion Criteria: Baseline Pre-weaning Biopsy findings Conducive to the Minimization of IS*

COMPARTMENT	FINDINGS
Portal inflammation and interface activity	This is preferably absent, but minimal to focal mild portal mononuclear inflammation may be present. Interface necro-inflammatory activity is absent or equivocal/minimal and, if present, involves a minority of portal tracts and not generally associated with fibrosis.
Centrilobular/perivenular inflammation	Negative for perivenular inflammation.
Bile duct changes	Lymphocytic bile duct damage, ductopenia, and biliary epithelial senescence changes are absent unless there is an alternative, non-immunological explanation (e.g. biliary strictures).
Fibrosis**	Fibrosis (if present) should be mild overall, and portal-to-portal bridging should not be more than rare. Perivenular and peri-sinusoidal fibrosis should not be more than mild according to the Banff criteria.
Arteries	Findings for obliterative or foam cell arteriopathy are negative.

*Patients with underlying AIH, HCV, PBC, or PSC are excluded⁴.

**Fibrosis should be graded as follows⁶⁷:

- **Portal/periportal:** 0 – 3
- **Peri-sinusoidal:** 0 – 3
- **Perivenular:** 0 – 3

4.2.2 Living Donor

Living donor participants who meet any of the following criteria will not be eligible for this study:

1. Any medical condition, such as anemia, coagulopathy, etc., that in the opinion of the principal investigator would interfere with safe participation in the trial.

4.3 PREMATURE TERMINATION OF A PARTICIPANT FROM THE STUDY

Participants may be prematurely terminated from the study for the following reasons:

1. The participant elects to withdraw consent from all future study activities, including follow-up.
2. The participant is “lost to follow-up” (i.e., no further follow-up is possible because attempts to re-establish contact with the participant have failed).
3. The participant dies.
4. Any participant who fails screening and is deemed ineligible to initiate immunosuppression withdrawal; such a participant will be considered a screen failure.

4.3.1 Follow-up for Participants Prematurely Terminated from the Study

Participants who wish to withdraw consent prior to completing immunosuppression withdrawal will be asked to complete the safety follow-up schedule specified in Appendix 3. If they decline they will be asked to undergo a study termination visit containing the assessments listed in Appendix 3, Visit 301. If

they decline they will be terminated with no further study data collection. Participants who fail screening and never initiate immunosuppression withdrawal will have no further follow up.

Participants who wish to withdraw consent after successfully completing immunosuppression withdrawal will be asked to complete the post withdrawal follow-up schedule specified in Appendix 2. If they decline they will be asked to undergo a study termination visit containing the assessments listed in Appendix 2, Visit 201.

5. STUDY MEDICATIONS

5.1 INVESTIGATIONAL MEDICATION

This section left intentionally blank.

5.2 CONCOMITANT MEDICATIONS

5.2.1 Prophylactic Medications

Prophylaxis against fungal and *Pneumocystis pneumonia* infection should be considered for participants who receive high dose corticosteroids for treatment of rejection according to each center's standard of care.

Participants who receive depleitional antibody therapy such as ATG or alemtuzumab for the treatment of severe rejection must receive prophylaxis against fungal, *pneumocystis*, and *cytomegalovirus* infection for a minimum of 12 weeks after completion of antibody therapy with medications prescribed according to each center's standard of care.

5.2.2 Other Medications

All immunosuppressive medications and any antibiotics, antimicrobials, and antifungals taken by or administered to study participants 30 days before their enrollment and throughout their study participation will be collected.

5.2.3 Prohibited Medications

- Short (≤ 7 days) courses of oral corticosteroids are permitted only for the treatment of unrelated illnesses such as asthma, allergy, etc. These should be avoided unless absolutely necessary.
- Otherwise, all immunosuppressive medications other than those used as specified in the protocol are prohibited during immunosuppression withdrawal unless rejection is suspected or diagnosed.
- Topical or inhaled corticosteroids or steroid mouthwashes will not be considered immunosuppressive medications.
- All live vaccines are prohibited for the duration of the trial.

6. STUDY PROCEDURES

6.1 VISIT WINDOWS

6.1.1 Scheduled Visits

Appendices 1 through 5-C present the schedule of events for this trial. See Section 6.2 to determine which schedules of visits to follow during the COVID-19 pandemic.

Visit 0 must occur within 56 days of Visit -1. Visit -1 may be done over multiple days following informed consent. The eligibility biopsy should be performed within 10 days of initiating Visit -1.

All other scheduled study visits must occur within the time limits specified below:

- Visit 101: within 7 days of Visit 0.
- Visit 201: Participants who initiate and successfully complete immunosuppression withdrawal should begin post withdrawal follow-up within 2 weeks of the date of completion of the participant's last taper level (see section 3.1.3).
- Visit 301: Participants who initiate but fail to successfully complete immunosuppression withdrawal (see Section 3.1.3.5) should begin safety follow-up within 2 weeks of the date of immunosuppression withdrawal failure.
- Visit RIS6: Participants who successfully complete immunosuppression withdrawal but then restart immunosuppression treatment will complete one additional follow-up visit as outlined in Appendix 4, in addition to post withdrawal follow-up, 26 weeks after immunosuppression is restarted. Appendix 2 visits should continue to occur according the participant's post withdrawal follow-up schedule. For the duration of the COVID-19 pandemic, do not conduct Visit RIS-6.
- Telephone consultations and laboratory evaluations done locally, outside of transplant center study visits, should be completed within:
 - \pm 5 days of the scheduled time points during immunosuppression withdrawal;
 - \pm 5 days of the scheduled time points within the first 26 weeks after completing immunosuppression withdrawal;
 - \pm 7 days of the scheduled time points during follow-up weeks 26-52;
 - \pm 14 days of the scheduled time points after 52 follow-up weeks.
- Up to 3 nonconsecutive pauses (up to 4 weeks each) may occur during Visits 101-111 (if needed) as outlined in section 3.1.3.4.
- All non-biopsy visits to the transplant center throughout the study should be completed within \pm 2 weeks of the scheduled time points listed in Appendices 1 through 5-C. Biopsy Visits 204 and 208 should be completed within \pm 4 weeks of the scheduled time points listed in Appendix 2. For

the duration of the COVID-19 pandemic, Biopsy Visit 208 should be completed -4 weeks to +6 months of the scheduled time point listed in Appendix 2-C.

- If a participant needs a for-cause biopsy within 8 weeks prior to a scheduled protocol visit, complete all clinical and mechanistic assessments listed in Appendix 5 at the time of the for-cause biopsy.
 - If the scheduled protocol visit occurs during Appendix 1A, complete all clinical assessments noted for the Appendix 1A visit but do not complete any mechanistic collections.
 - If the scheduled protocol visit is listed in Appendices 2-4, the for-cause biopsy visit will take the place of the scheduled protocol visit.
- If the Appendix 4 visit occurs within 1 month (4 weeks) of a scheduled protocol Appendix 2 visit, complete the Appendix 2 visit while collecting all mechanistic samples listed in the Appendix 4 visit in lieu of completing an additional visit.

Table 4. Frequency of Liver Function Tests

Population	Timing	Frequency
For all participants who initiate immunosuppression withdrawal	During immunosuppression withdrawal	Every 3 weeks*
	≤ 26 weeks post immunosuppression withdrawal	Every 4 weeks
	26-52 weeks post immunosuppression withdrawal	Every 8 weeks
	> 52 weeks post immunosuppression withdrawal	Every 12 weeks
	During Rejection	Liver function tests after the rejection episode per standard of care until resolution as determined by the investigator
Additional assessment for participants who successfully complete immunosuppression withdrawal and then restart immunosuppression therapy	26 weeks post immunosuppression restart	Once

*Every 2 weeks between Visits 103-105.

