6.2 COVID-19 PANDEMIC SCHEDULE OF EVENTS

During the pandemic, participants should follow the COVID-19 schedule of events (Appendices 2-C, 3-C, and 5-C) to prioritize critical safety follow-up visits and assessments following completion or discontinuation of immunosuppression withdrawal. Site investigators should ensure that all research activities are conducted in accordance with state, local, and institutional guidance. Each institution will

ensure that standard COVID-19 screening and precautions are in place before any on-site study visits or when participants resume the regular schedule of events.

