9.2.1 Primary Endpoint

The primary endpoint is defined in section 3.3.1.

The primary endpoint will be analyzed using the ITT sample and descriptively summarized with a point estimate and two-sided, 95% confidence interval. All participants who failed to complete immunosuppression withdrawal, regardless of reason, will be considered to have failed the primary endpoint. Participants without a biopsy 52 weeks following completion of immunosuppression withdrawal or who resume immunosuppression prior to 52 weeks will be considered to have failed the primary endpoint. This endpoint will also be analyzed using the PP sample.

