APPENDIX 2. SCHEDULE OF EVENTS – POST WITHDRAWAL FOLLOW-UP

IMPORTANT NOTE: For the duration of the COVID-19 pandemic, follow the COVID-19 Modified Appendix 2-C instead (per Section 6.2).

IS Withdrawal Follow-up Weeks ¹	0	13	26	52	78	104	130	156
Visit Number ^{2,3}	201 ⁴	202	203	204	205	206	207	208
General Assessments								
Limited physical exam	X	X	X	X	X	X	X	X
Vital signs including weight	X	X	X	X	X	X	X	X
Quality of Life Questionnaires	X		X	X	X	X	X	X
Status Change since prior visit ⁵	X	X	X	X	X	X	X	X
Telephone consultation ⁶	X							X
ECG					Prior to restarting tacrolimus ⁷			
Local Clinical Laboratory Assessments								
LFTs ⁸		Every 4 weeks		Every 8 weeks			Every 12 weeks	
CBC w/differential	X	X	X	X	X	X	X	X
Comprehensive metabolic panel, includes LFTs	X	X	X	X	X	X	X	X
Liver biopsy				X				X
Mechanistic Laboratory Assessments								
Frozen PBMC collection	X		X	X		X		X
Serum collection	X		X	X		X		X
Whole blood collection	X		X	X		X		X
Urine pellet collection	X		X	X		X		X
Fecal collection ⁹	X		X	X		X		X
Liver biopsy collection				X				X

¹ The assessments outlined in Appendix 2 should be completed for all participants who initiated and successfully completed immunosuppression withdrawal. Follow-up should begin within 2 weeks of the date of completion of the participant's last taper level (see section 3.1.3).

² If a for-cause liver biopsy is needed, follow all assessments specified in Appendix 5. If the for-cause biopsy occurs within 8 weeks prior to a scheduled protocol visit, complete all clinical and mechanistic assessments listed in Appendix 5 at the time of the for-cause biopsy. The for-cause biopsy visit will take the place of the scheduled protocol visit.

³ If a participant restarts immunosuppression after successfully completing immunosuppression withdrawal, follow the assessments listed in Appendix 4. **Appendix 2 visits to be completed in addition and concurrently with Appendix 4.**

⁴ For any participant requesting early termination from the study, follow all assessments specified here, Visit 201.

⁵ Includes assessment of change in adverse events and concomitant medications. Changes should be recorded in eCRFs as appropriate.

⁶ Complete following the performance of each liver function test assessment done outside of a transplant center clinical visit; AEs and concomitant medications to be reviewed.

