APPENDIX 2-C. (COVID-19 MODIFIED) SCHEDULE OF EVENTS – POST WITHDRAWAL FOLLOW-UP

IS Withdrawal Follow-up Weeks ¹	0	13	26	52	78	104	130	156
Visit Number ²	201 ³	202	203	204	205	206	207	208
General Assessments								
Limited physical exam								X
Vital signs including weight								X
Quality of Life Questionnaires ⁴				X	X	X	X	X
Status Change since prior visit								X
Telephone consultation ⁵	X							X
ECG				Prior to restarting tacrolimus ⁶				
Local Clinical Laboratory Assessments								
LFTs ⁷				Every 8 weeks		Every 12 weeks		
CBC w/differential			X	X	X	X	X	X
Comprehensive metabolic panel, includes LFTs			X	X	X	X	X	X
Liver biopsy								X
Mechanistic Laboratory Assessments								
Frozen PBMC collection								X
Serum collection								X
Whole blood collection								X
Urine pellet collection								X
Fecal collection								X
Liver biopsy collection								X

¹ The assessments outlined in Appendix 2 should be completed for all participants who initiated and successfully completed immunosuppression withdrawal. Follow-up should begin within 2 weeks of the date of completion of the participant's last taper level (see section 3.1.3).

² If a for-cause liver biopsy is needed, follow Appendix 5.

³ For any participant requesting early termination from the study, collect the following assessments if possible: telephone consultation with AE and concomitant medication update, CBC with diff, and comprehensive metabolic panel including LFTs.

⁴ Complete Quality of Life assessment by mail.

⁵ Complete following the performance of each liver function test assessment done outside of a transplant center clinical visit; AEs and concomitant medications to be reviewed.

⁶ For participants who need to restart tacrolimus for biopsy-confirmed or presumed acute rejection (see section 6.8). A follow-up ECG will be performed within 7 days after tacrolimus has been restarted. ECG findings will be monitored per the site's standard of care until the participant is taking a stable dose of tacrolimus. Evidence of a prolonged QTc interval will be appropriately evaluated and treated.

⁷ If participant experiences a rejection episode, complete liver function tests per standard of care until resolution as determined by the investigator. Record all liver function tests performed during a rejection episode in EDC.

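### The pandemic schedule has no week-52 biopsy, a missing week-52 biopsy counts as failure, and the plan does not say how the two rules meet

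*Protocol*

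**What the plan says.** **Regular schedule.** Protocol Appendix 2 places liver biopsies at week 52 (Visit 204) and week 156 (Visit 208). Section 6.1.1 asks for both within "4 weeks of the scheduled time points listed in Appendix 2".

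**Pandemic schedule.** The note at the head of Appendix 2 says: "For the duration of the COVID-19 pandemic, follow the COVID-19 Modified Appendix 2-C instead (per Section 6.2". Section 6.2 repeats the instruction: "participants should follow the COVID-19 schedule of events (Appendices 2-C, 3-C, and 5-C". In Appendix 2-C the biopsy row reads "Liver biopsy X": a single mark, in the week-156 column. Blood counts and metabolic panels are marked from week 26 onward and questionnaires from week 52. The only pandemic biopsy window in 6.1.1 is for Visit 208: "Biopsy Visit 208 should be completed -4 weeks to +6 months of the scheduled time point listed in Appendix 2-C".

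**Scoring.** Sections 3.3.1 and 6.9 still rest on the week-52 biopsy. Under protocol 9.2.1, "Participants without a biopsy 52 weeks following completion of immunosuppression withdrawal" are failures on the primary endpoint. SAP 7.2.1 labels lack of that biopsy non-tolerant.

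**Partial relief.** SAP 7.2.1 also uses a primary endpoint biopsy taken after the 4-week allowance, with no outer limit, and accepts a for-cause biopsy from the 8 weeks before Visit 204. SAP 7.1.2 includes data whatever the time of assessment unless stated otherwise. Section 6.2 foresees participants returning to the regular schedule.

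**The concern.** Scoring missing as failure is a reasonable conservative rule when a biopsy is missing because of the participant's course. Here the protocol's own substitute schedule leaves the biopsy out. Following the plan correctly could therefore produce a failure that says nothing about the graft, and the error runs in one direction only, lowering the tolerance proportion.

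The label also travels. SAP Table 7-2 reports fibrosis, eGFR and both quality-of-life instruments by tolerance status, and the logistic model for age and time post-transplant has tolerance as its outcome. The SAP gives no other definition of tolerance status than 7.2.1, so these participants would sit in the non-tolerant group there too.

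**Working it through.** **1. Does Appendix 2-C omit Visit 204?** The regular biopsy row has two marks (weeks 52 and 156); the pandemic row has one. Column positions come from extracted text, but the physical examination, vital signs and mechanistic sample rows of Appendix 2-C also carry a single mark in the same final column, and 6.1.1 names only Visit 208.

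**2. Does the schedule provide for participants before week 52?** Appendix 2-C marks blood tests at weeks 26 and 52 and keeps liver tests every 8 weeks, the frequency Table 4 gives for weeks 26 to 52. Appendix 3-C, by contrast, has visit marks only from week 104. This suggests, without proving it, that some participants were expected to pass week 52 under Appendix 2-C.

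**3. Do the existing provisions close the gap?**
- Late biopsy: no catch-up for Visit 204 is scheduled. The next scheduled biopsy is at week 156, which is 156 − 52 = 104 weeks later, and may be up to 6 months after that. The SAP does not say whether it can serve.
- For-cause biopsy: this requires allograft dysfunction (6.6.1, 6.10.1), so a stable participant is the least likely to have one.
- Per-protocol analysis: following Appendix 2-C is not a deviation, and the same scoring rule applies.

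**4. Effect on the primary estimate.** Inputs: n = 60 and an expected 40%, hence x = 24 (protocol 9.3). The exact 95% interval runs from the 2.5% point of Beta(x, n − x + 1) to the 97.5% point of Beta(x + 1, n − x). For 24/60 this gives 27.6% to 53.5%, as the protocol states. Now let k truly tolerant participants be scored non-tolerant, so the estimate is (24 − k)/60. The documents do not give k; the values below are assumptions.

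| k | Estimate | Exact 95% interval |
|---|---|---|
| 0 | 24/60 = 40.0% | 27.6 to 53.5 |
| 1 | 23/60 = 38.3% | 26.1 to 51.8 |
| 2 | 22/60 = 36.7% | 24.6 to 50.1 |
| 3 | 21/60 = 35.0% | 23.1 to 48.4 |
| 6 | 18/60 = 30.0% | 18.8 to 43.2 |

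The loss per participant is 1/60 = 1.7 points. If the biopsies are done later, accepted and favourable, the estimate returns to 24/60.

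**5. Biomarker comparison, conditional only.** With the protocol's difference of 0.1155 and SD of 0.152, a two-sided t-test with 24 versus 36 has power 0.809 (the protocol gives 0.808). If, and only if, the k participants join the 36, the mean difference shrinks by the factor 1 − k/(36 + k). For k = 3 it becomes 0.1155 × 36/39 = 0.1066. With 21 versus 39 and the SD adjusted for the mixture, power is 0.710.

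**The case against.** A reader might infer that everyone who passes week 52 under the pandemic schedule fails the primary endpoint. The documents do not support that. The SAP's late-biopsy and for-cause provisions can rescue some participants, others may return to the regular schedule, and those who reject or resume immunosuppression fail anyway. Failure for an administrative reason needs all three conditions: off immunosuppression, free of rejection, and no biopsy accepted.

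It can also be argued that Visit 204 was never cancelled, since 6.1.1 still lists it within 4 weeks of the Appendix 2 time point and 6.10.1 points to Appendix 2 for protocol biopsies. A Visit 208 window alone would fit equally well if nobody still needed a Visit 204 biopsy, and the week-26 marks may simply have been carried over. This stands as a doubt about how many were affected. It does not remove the conflict, because 6.2 and Appendix 2 direct participants to a schedule without that biopsy.

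A further tempting inference is that the primary biomarker comparison is contaminated. That is not established. Section 3.3.1 compares tolerant participants with those who fail withdrawal, and the protocol's definition of failed withdrawal does not list a missing biopsy. SAP 7.2.1 ties its label for missing biopsies to the primary endpoint, and SAP section 2 leaves mechanistic analyses to a separate plan. What stands is that these participants' biomarker group is unclear.

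**Conclusion.** The gap is real but conditional. Appendix 2-C omits the week-52 biopsy without a catch-up, while the endpoint definition and both scoring rules depend on it and make no exception. The supported size is 1.7 points of downward bias per truly tolerant participant left without an accepted biopsy. The total is unknown; the scenarios with two or three participants are illustrations, not estimates. The conclusion rests on reading the extracted biopsy row as a single week-156 mark and on at least one participant having passed week 52 under Appendix 2-C. If none did, one sentence in the SAP saying so settles the matter.

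**What to change.** 1. Reconcile protocol 6.1.1, Appendix 2-C, 3.3.1 and 9.2.1 and SAP 7.2.1 on the status of Visit 204 during the pandemic.
2. In SAP 7.2.1, class a Visit 204 biopsy not done under Appendix 2-C as administratively missing. Keep the late-biopsy rule, but state the latest biopsy accepted and whether Visit 208 can serve. A limit is needed because a week-156 biopsy does not measure tolerance at week 52.
3. Keep missing-as-failure as the primary, conservative analysis. Report the number affected and show the primary proportion twice: with these participants counted as non-tolerant, and as tolerant. Restrict the second count to those off immunosuppression and without rejection through week 52.
4. Leave them out of the tolerant versus non-tolerant contrasts, at least as a sensitivity analysis, and state their group for the biomarker comparison.

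The cost is SAP wording, one extra table row and a slightly smaller N in the contrasts. The analysis changes require no additional biopsies.
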